6.4. Covariates and Subgroups

As well as treatment group, subjects will additionally be classified by baseline flavivirus immune status, defined primarily as follows:

- ZIKV Seropositive: any subject with detectable ZIKV antibodies pre-vaccination
- ZIKV Seronegative: any subject without detectable ZIKV antibodies pre-vaccination

Baseline flavivirus immune status will then be further classified into the following groups:

- ZIKV Seropositive and DENV Seropositive
- ZIKV Seropositive and DENV Seronegative
- ZIKV Seronegative and DENV Seropositive
- ZIKV Seronegative and DENV Seronegative

If a subject has inconclusive results for baseline flavivirus immune status, they will not be summarized with either subgroup defined above but will be included in summaries of all subjects pooled.

Subgroups based on baseline flavivirus immune status will be used in analysis of the secondary and exploratory endpoints only. For all tables and figures presenting group-aggregate analyses by subgroup—or any columns, rows, or panels within them—a single stratum must include at least two subjects in order to be generated.

6.5. Missing Data

No imputation will be performed for missing values. Missing data are assumed to be missing completely at random.

6.6. Interim Analyses and Data Monitoring

This study has 3 planned interim analyses as described in Section 6.2. Summaries described for the second and third interim reports were combined into a single report thus a total of 2 interim analyses were actually performed. The analyses performed for the interim analyses were described in “Interim Statistical Analysis Plan for DMID Protocol: 16-0034 v0.1.” No unblinding of any individual subject treatment will be released in any interim analysis. Interim analyses will not include any formal hypothesis testing. They will, however, be made available to the study team and may impact the course of this study, be published, or be used in the planning of future studies.

6.7. Multicenter Studies

Not applicable.

6.8. Multiple Comparisons/Multiplicity

No adjustments for multiple comparisons/multiplicity were planned.

7. STUDY SUBJECTS

7.1. Disposition of Subjects

A flowchart showing the disposition of study subjects, adapted from the CONSORT Statement will be included in [Figure 1](#). This figure will present the number of subjects assessed for eligibility, randomized, terminated early, and included in the safety, immunogenicity, and per protocol populations. The CONSORT diagram will be presented by treatment group.

The disposition of subjects in the study will be tabulated by treatment group ([Table 11](#)). The table will include the number of subjects screened, enrolled/randomized, vaccinated, discontinued dosing, terminated early, completed follow-up and completed the study per-protocol. [Listing 2](#) includes subjects who terminated early or discontinued from the study.

Between-group comparisons of the numbers of subjects overall and by baseline flavivirus status who withdrew early and the numbers who discontinued treatment (i.e., did not receive the second dose) will be presented in [Table 12](#) using Fisher's exact 2-tailed test.

The number and percent of subjects excluded from each analysis population will be presented in [Table 13](#) by treatment group and reason for exclusion. The number of subjects included in each immunogenicity summary will be presented in [Table 14](#) by analysis population, treatment group, and immunogenicity time point. A listing of subjects excluded from analysis populations is available in [Listing 5](#).

Dates of first treatment administration will be listed by treatment group in [Table 15](#) and reasons for screen failure will be summarized in [Table 16](#).

7.2. Protocol Deviations

A summary of subject-specific protocol deviations will be presented by the reason for the deviation, the deviation category, and treatment group for all subjects ([Table 10](#)). All subject-specific protocol deviations and non-subject-specific protocol deviations will be included as data listings ([Listing 3](#) and [Listing 4](#)).

8. IMMUNOGENICITY EVALUATION

8.1. Primary Immunogenicity Analysis

Not applicable.

8.2. Secondary Immunogenicity Analyses

8.2.1. ZIKV Microneutralization Antibodies (MN50)

Seropositivity rates will be calculated based on ZIKV MN50 titers ≥ 10 and ≥ 100 . Seroconversion rates will be calculated based on the number of subjects experiencing at least a 4-fold rise in ZIKV MN50 titers from baseline.

Geometric mean titer (GMT) and 95% CI for ZIKV MN50 results at each visit and for peak titer results will be summarized by treatment group overall and by baseline flavivirus immune status for the immunogenicity (IMM) population in [Table 20](#) and per protocol (PP) population in [Table 21](#).

Geometric mean fold rise from baseline (GMFR) and 95% CI results at each post-baseline visit and for each subject's peak ZIKV MN50 titer results will be summarized by treatment group overall and by baseline flavivirus immune status for the IMM population in [Table 22](#) and PP population in [Table 23](#).

Seropositivity rates and 95% CIs at each visit and for peak ZIKV MN50 titer results will be summarized by treatment group overall and by baseline flavivirus immune status for the IMM population in [Table 24](#) and PP population in [Table 25](#).

Seroconversion rates and 95% CI at each post-baseline visit and using peak titer results will be presented by treatment group overall and by baseline flavivirus immune status for the IMM population in [Table 26](#) and PP population in [Table 27](#). Denominators for percentages will be the number of subjects with non-missing data at the applicable time point and 95% CI will be calculated using Clopper-Pearson methodology from a binomial distribution.

Graphical presentations of immune response by treatment group and baseline flavivirus immune status will include reverse cumulative distribution curves ([Figure 2](#) through [Figure 11](#) and longitudinal presentation of GMTs ([Figure 16](#) and [Figure 17](#)), seropositivity at a threshold of ≥ 10 ([Figure 18](#) and [Figure 19](#)), seropositivity at a threshold of ≥ 100 ([Figure 20](#) and [Figure 21](#)), and percent seroconversion ([Figure 22](#) and [Figure 23](#)).

A listing of ZIKV MN50 titers by subject, treatment group, baseline flavivirus immune status, planned time point, and actual study day is presented in [Listing 8](#).

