## 11 STATISTICAL CONSIDERATIONS

### 11.1 Study Hypotheses:

The primary goal of this study is to assess and compare the safety and reactogenicity of a homologous prime boost regimen of ZPIV given at two different dose levels in a population living in a flavivirus/ZIKV endemic area. Secondary goals are to explore the humoral responses to ZIKV after each vaccination in subjects with and without pre-existing flavivirus/ZIKV immunity. Blood samples are also collected for measuring ZIKV-related cellular and humoral immunity and systems biology in future assays. Enhanced surveillance for febrile and rash illness after signing the ICF will be performed to obtain preliminary data on the incidence and clinical presentation of naturally occurring flavivirus infections after vaccination. This study, like other Phase I studies, is exploratory rather than confirmatory, and thus the objective is not to formally test any test hypotheses, though comparisons between vaccine and placebo and between dose levels will be made. In addition, comparisons will be stratified by pre-vaccination flavivirus immune status of the volunteer and outcomes of flavivirus-naïve and flavivirus immune volunteers will be compared.

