3. STUDY OBJECTIVES AND ENDPOINTS

3.1. Study Objectives

Primary Objectives:

1. Assess the safety and reactogenicity of a homologous prime boost regimen of ZPIV given at two different dose levels in a dose de-escalation format in healthy adult subjects who live in Puerto Rico, a flavivirus endemic area.
2. Compare the safety and reactogenicity profile of ZPIV after each vaccination, between dosage groups, and by pre-vaccination flavivirus immune status.

Secondary Objectives:

1. Assess the humoral immune response to a homologous prime-boost regimen of ZPIV after each dose of vaccine as determined by kinetics of the immune responses, seroconversion rates, and Geometric Mean Titers (GMT) overall, and compare results between dosage groups and by pre-vaccination flavivirus immune status.
2. Assess the durability of the humoral immune response to ZPIV at 6, 12, 18, and 24 months after the second vaccine administration overall, and compare results between dosage groups and by pre-vaccination flavivirus immune status.

Exploratory Objectives

1. Estimate the incidence of ZIKV and DENV infections between Visit 00 and the subject's last visit and describe the clinical presentation including disease severity overall, by dosage group, product received, and pre-vaccination flavivirus immune status.

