4.4.4. Selection of Doses in the Study

Experience with licensed flavivirus vaccines suggests a 5 mcg dose should be safe and immunogenic; the 5 mcg dose was safe and protective in a NHP model [1]. Therefore, for this trial, subjects were enrolled initially in the 5 mcg group. To determine if lower doses of ZPIV are equally or comparably immunogenic to the 5 mcg dose, subjects were then enrolled in the 2.5 mcg group.

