8.2.2. ZIKV ELISA Antibodies

Seropositivity rates will be calculated based on ZIKV IgG ELISA titers ≥ 200 and ≥ 600 . Seroconversion rates will be calculated based on the number of subjects experiencing at least a 4-fold rise in ZIKV IgG ELISA titers from baseline.

The analyses described in Section [8.2.1](#) will be repeated for ZIKV ELISA titers: GMT and 95% CI results are presented in [Table 28](#) (IMM) and [Table 29](#) (PP), GMFR and 95% CI results are presented in [Table 30](#) (IMM) and [Table 31](#) (PP), seropositivity rates and 95% CIs are presented in [Table 32](#) (IMM) and [Table 33](#) (PP), and seroconversion results and 95% CIs are presented in [Table 34](#) (IMM) and [Table 35](#) (PP). Denominators for percentages will be the number of subjects with non-missing data at

the applicable time point and 95% CI will be calculated using Clopper-Pearson methodology from a binomial distribution.

Graphical presentations of immune response by treatment group and baseline flavivirus immune status will include reverse cumulative distribution curves ([Figure 24](#) through [Figure 35](#)) and longitudinal presentation of GMTs ([Figure 38](#) and [Figure 39](#)), seropositivity at a threshold of ≥ 200 ([Figure 40](#) and [Figure 41](#)), seropositivity at a threshold of ≥ 600 ([Figure 42](#) and [Figure 43](#)), and percent seroconversion ([Figure 44](#) and [Figure 45](#)).

A listing of ZIKV ELISA titers by subject, treatment group, baseline flavivirus immune status, planned time point, and actual study day is presented in [Listing 8](#).

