14.2 Immunogenicity Data

ZIKV Microneutralization Titers

Table 20: ZIKV Microneutralization Antibody (MN50) Geometric Mean Titer (GMT) Results with 95% Confidence Intervals by Time Point, Treatment Group, and Baseline Flavivirus Immune Status – Immunogenicity Population

[Implementation note: If a baseline flavivirus subgroup includes fewer than 2 subjects, the GMT and 95% CI fields will be populated with 'N/A'.]

Time Point	Baseline Flavivirus Immune Status	2.5 mcg ZPIV			5 mcg ZPIV			Placebo		
		n	GMT	95% CI	n	GMT	95% CI	n	GMT	95% CI
Baseline	All Subjects	x	xx	xx.x, xx.x	x	xx	xx.x, xx.x	x	xx	xx.x, xx.x
	Baseline ZIKV Seropositive									
	Baseline ZIKV Seronegative									
	Baseline ZIKV Seropositive and DENV Seropositive									
	Baseline ZIKV Seropositive and DENV Seronegative									
	Baseline ZIKV Seronegative and DENV Seropositive									
	Baseline ZIKV Seronegative and DENV Seronegative									

Repeat Baseline for:

Day 29 (Pre-Dose 2)										
Day 57 (28 Days Post-Dose 2)										
Day 209 (180 Days Post-Dose 2)										
Day 750 (721 Days Post-Dose 2)										
Peak Post-Baseline										

n = Number of subjects in the immunogenicity population with non-missing immunogenicity data at the specified time point.

95% CI = 95% confidence interval based on Student's t-distribution.

Table 21: ZIKV Microneutralization Antibody (MN50) Geometric Mean Titer (GMT) Results with 95% Confidence Intervals by Time Point, Treatment Group, and Baseline Flavivirus Immune Status – Per Protocol Population

Table 22: ZIKV Microneutralization Antibody (MN50) Geometric Mean Fold Rise (GMFR) Results with 95% Confidence Intervals by Time Point, Treatment Group, and Baseline Flavivirus Immune Status – Immunogenicity Population

[Implementation note: baseline results are not included in this table.]

Table 23: ZIKV Microneutralization Antibody (MN50) Geometric Mean Fold Rise (GMFR) Results with 95% Confidence Intervals by Time Point, Treatment Group, and Baseline Flavivirus Immune Status – Per Protocol Population

[Implementation note: baseline results are not included in this table.]

Table 24: ZIKV Microneutralization Antibody (MN50) Seropositivity Results with 95% Confidence Intervals by Time Point, Treatment Group, and Baseline Flavivirus Immune Status – Immunogenicity Population

[Implementation note: If a baseline flavivirus subgroup includes fewer than 2 subjects, the % and 95% CI fields will be populated with 'N/A'.]

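### Both secondary objectives call for a comparison of immune response between doses, but the SAP produces no between-dose estimate and no measure of its uncertainty

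*SAP*

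**What the plan says.** SAP 3.1 sets two secondary objectives, on the humoral response and on its durability. Each ends with an instruction to "compare results between dosage groups and by pre-vaccination flavivirus immune status". SAP 4.4.4 gives the reason for the second dose group: "To determine if lower doses of ZPIV are equally or comparably immunogenic to the 5 mcg dose". Protocol 11.1 disclaims formal hypothesis tests but adds that "comparisons between vaccine and placebo and between dose levels will be made".

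The analysis sections are written arm by arm. In SAP 8.2.1, GMT for MN50 "results at each visit and for peak titer results will be summarized by treatment group overall and by baseline flavivirus immune status". For seroconversion: "Seroconversion rates and 95% CI at each post-baseline visit and using peak titer results will be presented by treatment group overall". GMFR and seropositivity follow the same pattern. SAP 8.2.2 states that these analyses "will be repeated for ZIKV ELISA titers". The Table 20 shell has n, GMT and CI columns for each arm and the footnote "95% CI = 95% confidence interval based on Student's t-distribution". The Table 24 and 26 shells give counts, a percentage and a CI for each arm. SAP 8.1, 8.3 and 12 are marked as not applicable, and Protocol 11.4.3 is also limited to per-group summaries.

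**The concern.** An objective that says to compare two doses needs a quantity that expresses the comparison, such as a GMT ratio or a difference in proportions, with an interval around it. The plan reports two separate estimates and leaves the reader to combine them. What is at stake is the interpretation of the 2.5 mcg group. Without an interval for the contrast, the report cannot say how large a loss or gain in response is compatible with the data, and two similar-looking columns may be taken as evidence that the doses perform alike.

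The comparison is also not protected by randomisation. Subjects were randomised to ZPIV or placebo within a group, not between doses. SAP 4.4.3 describes Group 2 as randomised once Group 1 enrolment was complete, while Protocol Section 4 allows some overlap. In a largely flavivirus-immune population, a difference in baseline titre between the cohorts could carry into the post-dose titres. Baseline titre enters the plan within arm, through GMFR and seroconversion, but enters no between-dose estimate.

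**Working it through.** **1. The plan's own power figures.** The only ones (SAP Section 5) concern seeing at least one adverse event, 1 − (1 − p)^n.
- n = 35, p = 4.5%: 1 − 0.955^35 = 80.04%. Stated: at least 80%.
- n = 80, p = 2.0%: 1 − 0.98^80 = 80.14%. Stated: approximately 80%.

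Both reproduce. No figure is given for an immunogenicity contrast, and no margin, titre SD or baseline correlation.

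**2. Search for a contrast.** SAP 8.2.1, 8.2.2, Tables 14 and 20-35, the titles and notes of Figures 2-45 (the images were not available) and Protocol 11.3 to 11.4.3 contain no ratio, difference, model or test between doses. Elsewhere the SAP does compare groups: Fisher's exact and Wilcoxon tests between ZPIV doses for reactogenicity and adverse events (9.3.1, Table 43), and Fisher's exact test across the three treatment groups for withdrawals and discontinuations (7.1, Table 12).

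**3. Precision of a GMT ratio.** Input: about 35 evaluable ZPIV recipients per dose (Protocol 11.2). Half-width on the log10 scale = t(0.975, 68) × SD × √(2/35), with t = 1.996 and √(2/35) = 0.239. The SD is assumed.

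| Assumed log10 SD | Half-width | 95% CI factor (×/÷) |
|---|---|---|
| 0.3 | 0.143 | 1.39 |
| 0.4 | 0.191 | 1.55 |
| 0.5 | 0.239 | 1.73 |
| 0.6 | 0.286 | 1.93 |
| 0.8 | 0.382 | 2.41 |

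SAP 6.3.2 keeps subjects who lost pre-vaccination samples in the post-baseline analyses, so the 5 mcg number for GMT may lie between about 35 and 45. With 45 v 35 and SD 0.5 the factor is about 1.68.

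**4. What the contrast adds (invented data, SD 0.5, 35 per dose).** Per-arm GMTs of 100 (67 to 149) at 2.5 mcg and 200 (135 to 297) at 5 mcg have overlapping intervals. The 2.5/5 ratio is 0.50, with 95% CI 0.50 ÷ 1.73 to 0.50 × 1.73, or 0.29 to 0.87.

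For seroconversion, 18/35 (34 to 69%) and 28/35 (63 to 92%) also overlap, yet the difference is 29 points (Newcombe 95% CI 6 to 47). With 28/35 in both arms the difference is 0, with 95% CI −19 to +19 points. An apparent tie therefore leaves sizeable differences open.

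**5. Gain from baseline adjustment.** ANCOVA multiplies the half-width by about √(1 − r²), where r is the correlation of baseline and post-dose log titre. The factor is 1 at r = 0, 0.87 at r = 0.5 and 0.71 at r = 0.7. Neither document gives r. Titres below the LLOQ are set to 5 (SAP 3.3) and the population mixes serostatus groups, so the gain could be close to nothing.

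**The case against.** The best defence is that the SAP follows its endpoints. Primary endpoints 5 and 6 are worded as comparisons and receive tests. The four immunogenicity endpoints are worded as frequencies, titres or proportions by group and receive summaries. Protocol 11.4.3 is equally descriptive, and the study has no null hypothesis. Side-by-side estimates with intervals, supported by reverse cumulative and longitudinal plots, are a recognised Phase 1 form. A statistician could also rebuild an unadjusted ratio from the reported n, GMT and t interval.

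Much of this stands. No test is required, and the gap lies between objective and analysis in both documents, so it is not a departure of the SAP from the protocol. But the objectives do say to compare, an estimate with an interval needs no hypothesis, and a baseline-adjusted ratio cannot be rebuilt from the tables.

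Three stronger readings are tempting and are not supported:
- **That the doses will be judged by whether their intervals overlap.** With 35 per arm and equal SDs that rule would act as a two-sided test at about 0.0054. The SAP states no such rule, so the figure describes a reader's habit and not the plan.
- **That baseline titre goes unused although every analysed subject has one.** GMFR and seroconversion use it, and results are split by serostatus. Under SAP 6.3.2 some analysed subjects have no pre-vaccination sample.
- **That ANCOVA alone is a free repair.** It would drop the subjects that SAP 6.3.2 retains, and it cannot remove differences due to enrolment period.

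Timing also counts. SAP 6.2 dates the interim analyses 12DEC2018 and 22DEC2020, and SAP Section 15 cites a protocol version of 06 December 2021, so this SAP came later. Protocol 11.3.1 planned interim immunogenicity results by study treatment and made the interim analyses available to the study team.

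**Conclusion.** The point holds as a gap between objective and analysis: the plan promises a comparison between doses for both secondary objectives and yields no between-dose estimate or interval for any immunogenicity endpoint. It does not invalidate the per-arm results. With 35 per dose the missing interval would be a factor of 1.39 to 2.41 either side of the GMT ratio for an assumed log10 SD of 0.3 to 0.8. For seroconversion it would be about ±19 points if both arms were at an assumed 28/35. These are illustrations of precision, not properties stated in the documents.

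A reader might infer that adding the contrast would settle whether 2.5 mcg performs as well as 5 mcg. It would not: no margin is stated, the cohorts were not randomised against each other, and SAP 6.8 plans no multiplicity adjustment. The contrast would measure the uncertainty that the present tables leave implicit. This is a cheap improvement that should be made.

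**What to change.** In SAP 8.2.1 and 8.2.2, for MN50 and ELISA among ZPIV recipients, add:

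1. The 2.5/5 mcg GMT ratio with 95% CI from log10 titres, unadjusted, in all subjects with data, at Day 57 and the other reported post-dose visits.
2. The difference in seroconversion proportion between doses with a 95% CI, for example Newcombe.
3. As a supporting analysis, the GMT ratio from ANCOVA on baseline log10 titre, in subjects with a baseline sample, stating how many hurricane-affected subjects it drops.

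Label all three as exploratory, not randomised between doses because enrolment was largely sequential, unadjusted for multiplicity, added after the interim analyses, and unable to establish equivalence without a margin. Record the addition in SAP Section 15.

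The cost is SAP wording and a few more tables from data already collected. In the present layout, items 1 and 2 come to 2 assays × 2 populations × 2 measures = 8 tables, or extra columns in eight existing ones. Limiting them to the immunogenicity population halves that. The other cost is that the analysis is specified after group-level interim results were due to reach the study team, which the label must disclose.

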8.2.2. ZIKV ELISA Antibodies

Seropositivity rates will be calculated based on ZIKV IgG ELISA titers ≥ 200 and ≥ 600 . Seroconversion rates will be calculated based on the number of subjects experiencing at least a 4-fold rise in ZIKV IgG ELISA titers from baseline.

The analyses described in Section [8.2.1](#) will be repeated for ZIKV ELISA titers: GMT and 95% CI results are presented in [Table 28](#) (IMM) and [Table 29](#) (PP), GMFR and 95% CI results are presented in [Table 30](#) (IMM) and [Table 31](#) (PP), seropositivity rates and 95% CIs are presented in [Table 32](#) (IMM) and [Table 33](#) (PP), and seroconversion results and 95% CIs are presented in [Table 34](#) (IMM) and [Table 35](#) (PP). Denominators for percentages will be the number of subjects with non-missing data at

the applicable time point and 95% CI will be calculated using Clopper-Pearson methodology from a binomial distribution.

Graphical presentations of immune response by treatment group and baseline flavivirus immune status will include reverse cumulative distribution curves ([Figure 24](#) through [Figure 35](#)) and longitudinal presentation of GMTs ([Figure 38](#) and [Figure 39](#)), seropositivity at a threshold of ≥ 200 ([Figure 40](#) and [Figure 41](#)), seropositivity at a threshold of ≥ 600 ([Figure 42](#) and [Figure 43](#)), and percent seroconversion ([Figure 44](#) and [Figure 45](#)).

A listing of ZIKV ELISA titers by subject, treatment group, baseline flavivirus immune status, planned time point, and actual study day is presented in [Listing 8](#).

